High quality delivery of evidence-based psychosocial interventions (EBPIs) in primary care medicine is a function of many variables, including clinician training and ready access to EBPI decision support. Importantly, quality is also driven by the clinician's ability to implement the therapeutic elements of EBPIs to fidelity and with competence. Even when clinicians undergo rigorous training, and find the intervention components useful in care, clinicians significantly drift from the original protocol because the processes, structure and elements of care frequently clash with clinician productivity and the shifting needs of the patient populations they serve. Clinicians in low resource settings like federally qualified health centers (FQHCs) report that while elements of EBPIs are important, their design is cumbersome, complex, overwhelming, inflexible, and minimize the nonspecific factors clinicians feel are crucial for quality delivery of care. In short, EBPIs demonstrate low usability (i.e., the extent to which a product can be used by specified users to achieve specified goals with effectiveness, efficiency, and satisfaction in a specified context of use. Although many implementation science (IS) frameworks do address the importance of EBPI characteristics, adapting and modifying EBPIs to enhance usability has not been a focus. User centered design (UCD) approaches, which have been successful in creating hardware and software tools that are accessible and compelling to use, have the potential to modify EBPIs so that they are accessible and compelling to clinicians.

We hypothesize that UCD-driven modifications to EBPI usability will result in enhanced clinician ability to deliver EBPI elements competently (target), and that better competence results in better patient-reported outcomes. We will modify Behavioral Activation (BA) because it is the EBPI often used in primary care settings.

To prepare for a larger trial to test hypotheses regarding the impact of EBPI usability on uptake, fidelity and competence, the aims of Project 002 R34 are:

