when to use BA in specific clinical situations. The Therapists and Care Managers of some clinics in the BVHC network have already implemented this modified approach, and the goal is to have all clinics in the network learn and use the model. The Therapists and Care Managers will receive additional training and guidance from the study team to achieve this modification, but the patients' clinical care visits will not change. During the additional training, UW and Stanford study staff members will provide consultation on BVHC patient cases in order to provide support for any cases where BVHC clinicians are having difficulty using BA. During these discussions, no staff from the UW or Stanford team will ever know any identifiable information about the patients. However, both UW and Stanford staff members will have access to clinician participants' identifiable information from training/support activities with the clinicians. We will use pre-existing clinic measures to collect patient outcome data for patients whose providers are using the modified BA model. We will also collect patient outcomes using the same pre-existing clinic measures for patients whose providers are providing usual care. We will then compare outcome data for each type of care. A total of 11 clinicians and 80 patients will be recruited for Phase 3.

Clinician Procedures:

Clinician training in BA. UW team staff will train clinicians in modified Behavioral Activation elements per the protocol used by the AIMS Center, which includes training in basic brief treatment skills, therapeutic elements of the intervention and therapy process. The training will also include modifications developed via clinician/research staff co-design in Phase 2.

Note: These modifications will be developed in Phase 2, and new materials will be submitted to the IRB prior to beginning Phase 3.

Training will be followed by simulated case training. Once clinicians finish the training and begin using the modified BA with patients, we will use a self-report checklist and open-ended questions regarding the use of modified BA to measure clinicians' adherence to the model.

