Two types of data will be collected, clinician assessment of intervention usability, and clinician ability to learn the intervention and maintain competency. To measure intervention usability, clinicians will complete the AIM, FIM, IAM, the User Burden Scale and the System Usability Scale, which are core measures for this Center. These measures will be administered both pre- and post-. Clinicians may also be asked to complete exit interviews regarding their experience using the BA task-sharing model. These interviews may be video-recorded (with clinician consent) for later review.

To measure sustained competency, clinicians will use a self-report checklist of task-sharing BA components with each patient to ensure they are adhering to the model. Clinicians will also complete qualitative questions regarding model adherence at the end of the study.

We will conduct 3-month follow up interviews with clinicians to ask if they are still using the task sharing model, if they are using all aspects of the model, and if they have made any modifications to the model. These interviews may be video-recorded (with clinician consent) for later review.

Clinician procedures are summarized here:

- Complete updated consent form
- Complete full BA task-sharing training starting in January 2020

- 6 synchronous sessions (about 1 hour each)
- Complete asynchronous material in between sessions
- Staff will be paid \$50 for each of the 6 synchronous sessions they attend
- Complete pre-trial usability questionnaires re: BA task-sharing model, for which they will be paid \$25
- After BA task-sharing training is complete, begin using the model with clinic patients (target of 10 patients per clinic)
- Use a self-report checklist of task-sharing BA components with each patient to ensure they are adhering to the model
- Complete post-trial usability questionnaires re: BA task-sharing model, for which they will be paid \$25
- Possibly complete exit interviews re: their experience using the BA task-sharing model, for which they would be paid \$50. These interviews may be video-recorded (with clinician consent) for later review.
- Complete a 3-month follow up interview to report if/how they are still using the modified BA model, for which they will be paid \$50. These interviews may be video-recorded (with clinician consent) for later review.

Patient Procedures

Patient eligibility.

Patient participants will be identified through each clinic's electronic health record.

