- common problems clinicians experience or anticipate in **usability** of EBPIs such as: (1) too many steps in a typical session; (2) not enough time to “get to know” the patient/not enough time to get through the process of EBPI in each session; (3) too tiring to deliver on days when clinicians see patients back to back; (4) focusing on problems was not synergistic with clinic mandates to use strength-based interventions; (5) difficulty using EBPIs to address common problems, such as lack of motivation, affect regulation, profound pessimism, trauma exposure, and access to basic needs in the face of poverty (food, shelter, access to health care, safety); (6) insufficient support to know when adding other EBPI elements or eliminating EBPI elements was appropriate or in violation of protocol; and, (7) over insistence by trainers or supervisors to have clinicians structure sessions and use of forms.
- Implementation domains to include (1) intervention characteristics, including core components and adaptable, peripheral elements; (2) outer setting, the broader economic, political, social context in which an organization exists; (3) inner setting, the immediate organizational context in which implementation occurs, including shared receptivity to change; (4) individual characteristics of practitioners and implementation team members, such as personal and professional values, interests, and affiliations; and (5) the implementation process, the steps and modes by which active change is undertaken.
- Questions about what clinicians value about their work with their patients, what they feel is missing when using EBPIs, and suggestions for how it could be improved, given their clinical context and patient population.

Phase 3

Clinician Participants:

Clinician Training:

Adherence Scale (checklist) – to be developed in Phase 2

Intervention Usability:

- AIM (already uploaded to Zipline in “Assessments” pdf)
- IAM(already uploaded to Zipline in “Assessments” pdf)
- FIM (already uploaded to Zipline in “Assessments” pdf)
- User Burden Scale
- System Usability Scale
- Qualitative adherence questions
- Qualitative adherence/modification questions (at 3-month follow up)

Demographic Survey

Patient Participants:

- Demographic info (EHR)
- Process measures (eg. how long have patients been in treatment, how frequently do they have visits, etc.) – (EHR)
- 9-Item Patient Health Questionnaire (PHQ-9) – (EHR)
- 7-Item Generalized Anxiety Disorder (GAD-7) – (EHR)

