- **Clinician adherence scale/checklist:** We will use this self-report checklist to measure how closely clinicians are adhering to the modified Behavioral Activation (BA) model. This checklist will include the aspects of BA listed below and will ask clinicians to check off whether they have been using each aspect or not. The checklist may also include comment boxes for clinicians to add notes explaining why they did or didn't use a particular aspect. BA aspects for checklist will include:
 - Set an agenda
 - Help patient set goals
 - Identify barriers to setting goals, including: Avoidance, Negativity Bias, Affect Regulation, Distraction, Apathy, Reward Processing Dysfunction, Substance Use
 - Use learned strategies to address barriers with patient
- **Clinician qualitative adherence/modification questions (at 3-month follow up):** We will conduct follow up interviews 3 months after the trial to ask if clinicians if/in what manner they are still using the modified BA model. We will ask open-ended questions like:
 - Are you still using the modified BA model?
 - Are you using all aspects of the model, or only some?
 - Have you made any modifications to the model?
- **Patient qualitative treatment experience questions:** We will conduct exit interviews with up to 10 patient participants to capture their perspective and satisfaction with the care their providers delivered via the modified BA model. We will ask questions like:

- Are you satisfied with the quality of care that you received?
- Do you feel that your Therapist and Care Manager worked well together?
- Do you feel like you would have received better care by working with just one or the other, rather than with both?

5.15 Send HSD a [Confidentiality Agreement](#) if you will obtain or use any private identifiable UW records without subject’s written consent (for example, screening medical records or class grades to identify possible subjects).

The Confidentiality Agreement form must be completed, printed, signed, and mailed to the Human Subjects Division at Box 359470. Your IRB application cannot be approved until we receive the Confidentiality Agreement.

6 CHILDREN (MINORS) and PARENTAL PERMISSION

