13.2 Approvals and permissions. Identify any other approvals or permissions that will be obtained. For example: from a school, external site/organization, funding agency, employee union, UW Medicine clinical unit.

Do not attach the approvals and permissions unless requested by the IRB.

N/A

13.3 Financial Conflict of Interest. Does any member of the team have a Financial Conflict of Interest (FCOI) in this research, as defined by [UW policy GIM 10](#)?

No
Yes

→ If yes, upload the Conflict Management Plan for every team member who has a FCOI with respect to this research, to the **Supporting Documents** page of **Zipline**. If it is not yet available, use the text box to describe whether the Significant Financial Interest has been disclosed already to the UW Office of Research.

PROJECT SUMMARY. Evidence-based psychosocial interventions are rarely used in part because of their design complexity. Although many implementation frameworks do address the importance of EBPI characteristics, adapting and modifying EBPIs to enhance usability has not been a focus. User-centered design (UCD) approaches, which have been successful in creating hardware and software tools that are accessible and compelling to use, have the potential to modify EBPIs so that they are accessible and compelling to clinicians. We hypothesize that UCD driven modifications to EBPI usability (target mechanism) will result in enhanced clinician ability to deliver EBPI elements competently, and that better competence results in better patient reported outcomes. We will modify Behavioral Activation (BA), an EBPI often used in primary care, to function as a Task Sharing model between clinicians and care managers. Our specific aims are to (1) identify usability problems clinicians and care managers encounter with BA (2) create a clinician- and care manager-driven modification of BA and (3) compare the modified Task Sharing version of BA to usual care on usability, clinician competence, and patient reported outcomes.

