A final prototype will undergo initial feasibility evaluation in pilot field deployments with each clinician using the prototype with one patient. Once we have completed the redesign of BA so that it (1) meets needs of its clinicians and patients (i.e., is useful), and (2) is easy to use and understand (i.e., is usable), we will move to the *Test* phase of this study.

Phase 3/Aim 3: Test phase (15 months). We will conduct a pilot study comparing the modified version of BA to usual care. Therapists will be randomized to either modified BA, and will use their assigned intervention with 5 patients.

Patient eligibility. Patient participants will be identified through each clinic's electronic health record. Participants must be 18 years old or older, suffering from mild to moderate depression. The site champion will identify potential participants from their electronic health records (EHRs) who score between 10 and 20 on the PHQ-9 and will contact potentially eligible patients to conduct a preliminary screening for eligibility, provide a brief description of the study and obtain informed consent.

Clinician training in modified BA. [name] and [name] will train clinicians in the modified BA. We will follow the protocol developed by the AIMS Center, which includes training in basic brief treatment skills, therapeutic elements of the intervention and therapy process. This is followed by simulated case training.

Clinician data collection. Two types of data will be collected, clinician assessment of intervention usability, and clinician ability to learn the intervention and maintain competency. To measure **intervention usability**, clinicians will complete the ALFA-Q Acceptability Scale, the User Burden Scale and the System Usability Scale, which are core measures for this Center (see **Methods Core** for description of scales). **Learnability** of the interventions will be measured in number of role plays needed to reach competency during training. To measure **sustained competency**, clinicians will collect audio recordings of patient sessions for review by experts. Drs. [name] and [name] will conduct these reviews using each intervention's adherence scale. Sustained competency will be defined by (1) time to first session rated < 4 ("good") and (2) number of sessions rated < 4 ("good") once certified. Clinicians will not be given feedback on session performance.

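### The Phase 3 measure of sustained competency is a self-report adherence checklist, and the planned Fidelity/Competence analysis needs data that the procedures do not collect

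*Combined protocol and SAP*

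**What the plan says.** **Role of competence.** Section 1.5 and the Specific Aims hypothesise that redesign leads to "enhanced clinician ability to deliver EBPI elements competently (target") and that competence then improves patient outcomes. The Project Summary sets as its third aim to "compare the modified Task Sharing version of BA to usual care on usability, clinician competence, and patient reported outcomes".

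**IRB protocol, Phase 3.** Section 5.1 announces two kinds of clinician data: usability, and how well clinicians learn the intervention and stay competent in it. For the second it says: "To measure sustained competency, clinicians will use a self-report checklist of task-sharing BA components with each patient". End-of-study adherence questions and a 3-month interview are added. Section 5.14 describes the checklist as an instrument "to measure how closely clinicians are adhering to the modified Behavioral Activation (BA) model" that "will ask clinicians to check off whether they have been using each aspect or not". Section 5.2 lists it under clinician training as "Adherence Scale (checklist"), still to be developed. On training, section 5.1 says: "Training will be followed by simulated case training".

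**Research plan (Project Summary onward).** Under Clinician data collection, clinicians record patient sessions on audio and experts rate them. Sustained competency is the time to the first session rated below 4 and the number of sessions so rated after certification. Learnability is a separate measure, which "will be measured in number of role plays needed to reach competency during training". The Data analysis section then compares hours to certification (dotplot, *t*-test) and the proportion of sessions scored below 4 (two-sample proportion test), and adds a mediation summary with fidelity partialled out.

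**The concern.** Adherence and competence are different constructs. A tick shows that the clinician says an element was used. A session handled well and one handled badly give the same record if the same boxes are ticked, and the person being assessed completes the form. If the checklist result keeps the label of sustained competency, a reader of the pilot could take a well-filled checklist as evidence of skill.

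The second problem follows from the first. The analysis section is written for session scores and certification times that the Phase 3 procedures do not produce. At analysis the team would have to drop the competence results or put the checklist in their place without a stated rule. Aim 3 exists to inform a larger trial, and competence is part of the mechanism that trial would test, so the plan should settle now what the pilot can report about it.

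**Working it through.** No arithmetic applies. The plan gives no numerical target for competence and no power calculation for Aim 3, so the check is whether each planned analysis has a variable behind it.

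| Quantity needed by the research plan | Where it is needed | Source in the Phase 3 procedures (5.1, 5.2, 5.14) |
|---|---|---|
| Session score, to identify sessions below 4 | Clinician data collection; Data analysis | None. The checklist is used/not used per aspect. |
| Time to first session rated below 4 | Clinician data collection | None, as there is no session score. |
| Hours to reach certification | Data analysis | None. Section 5.1 sets six synchronous sessions of about an hour and records no time to a criterion. |
| Role plays to competency | Clinician data collection (learnability) | None. Simulated cases take place, but no count is listed. |
| The same measures under usual care | Data analysis, between-treatment tests | None. The checklist covers task-sharing components and is used by clinicians delivering that model. |
| Fidelity score to partial out | Data analysis, mediation summary | None. |

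All six rows are empty.

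**Could the checklist stand in?** Its listed aspects are agenda setting, goal setting, identifying barriers and using strategies to address them. Comment boxes may be added for why an aspect was or was not used. None of these grades quality. The end-of-study questions and the 3-month interview ask about adherence, continued use and modification, which bear on drift but not on skill.

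**Could the expert-rating route be carried out as the IRB protocol stands?** Not as described:
- Section 5.2 lists no recording or rating.
- Section 5.1 mentions Phase 3 recording only for clinician interviews, and section 5.5 only for clinicians and staff.
- Section 8.2 obtains no patient consent for clinical care sessions.
- Sections 5.5 and 9.1 give the university team de-identified patient data only, exit interviews aside, while section 9.6 treats voice recordings as identifying.

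**Which label does the plan itself use?** Section 5.1 (training paragraph), section 5.2 and section 5.14 all call the instrument an adherence measure. Only the sustained-competency sentence in 5.1 says otherwise, and its closing clause returns to adherence.

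**The case against.** The strongest reply is that this is mostly a labelling slip in a descriptive pilot. The checklist is called adherence almost everywhere. Aim 3's H1 and H2, in section 1.5 and the Specific Aims, do not include competence. The Data analysis section says the focus is descriptive and treats mediation as exploratory. The Project Summary attaches the mechanism label to usability, and the Significance section counts adherence as part of the mechanism. All of this is correct and lowers the weight of the point. It does not remove it: the Project Summary still promises a competence comparison with usual care, and the analysis section still specifies tests that have no data.

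A reader might go further in three ways that the documents do not support:
- **That the competence aim has no valid measure anywhere.** The research plan specifies expert review of recorded sessions and builds an analysis on it, and nothing withdraws that text. The defect is an unreconciled conflict between that text and the Phase 3 procedures.
- **That the loss can be put as a figure, such as a weakened correlation with patient outcome.** The plan gives no correlation between checklist, competence and outcome, so any figure would be assumed. Adherence may also relate to outcome in its own right.
- **That role plays to competency are the plan's measure of sustained competency.** The research plan uses that count for learnability.

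The checklist is also not final, so its content could change. As described, however, it has no quality rating.

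**Conclusion.** The point holds in this form: section 5.1 labels an adherence checklist as a measure of sustained competency, and the Fidelity/Competence analysis, including its between-treatment test and the fidelity-based mediation summary, cannot be run on the Phase 3 data listed. The size is structural: every quantity those analyses need is missing from section 5.2, and usual care has no comparator data.

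This rests on two assumptions: that section 5.2 is the full list of Phase 3 clinician variables, and that the uploaded forms, which are not part of the documents, add no skill rating. It should be corrected before the data are analysed. It does not affect the usability comparison or the patient symptom outcomes.

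**What to change.** Reconcile sections 5.1, 5.2 and 5.14 with the research plan's Clinician data collection and Data analysis sections:

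1. In section 5.1, call the checklist result self-reported adherence in clinicians using modified BA, and stop describing it as a measure of sustained competency. Bring the recorded-session definition in Clinician data collection into line.
2. In Data analysis, remove the session-score and certification-hours analyses and the mediation summary with fidelity partialled out, or replace them with a descriptive summary of self-reported adherence by clinician.
3. In the Project Summary, remove the competence comparison with usual care. State that neither sustained competence nor a between-condition contrast in competence is assessed.
4. Optionally, if trainers already run the simulated cases with each clinician individually, record the number of role plays to competency as the learnability measure. That would give the promised data on learning a variable. Section 5.1 does not say who runs or scores these cases and sets no threshold, so both would need stating.

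Steps 1 to 3 are wording changes, and step 4 adds one count per clinician. The cost is a narrower claim: the pilot would report what clinicians say they used and make no statement about skill. Keeping the expert-rated analysis instead would be a larger change, needing a rating variable, permission to record sessions and rated sessions under usual care.
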